8.2.2 RELATIONSHIP TO STUDY AGENT

For all collected AEs, the clinician who examines and evaluates the participant will determine the AE’s causality based on temporal relationship and his/her clinical judgment. The degree of certainty about causality will be graded using the categories below.

- Definitely Related – There is clear evidence to suggest a causal relationship, and other possible contributing factors can be ruled out. The clinical event, including an abnormal laboratory test result, occurs in a plausible time relationship to drug administration and cannot be explained by concurrent disease or other drugs or chemicals. The response to withdrawal of the drug (dechallenge) should be clinically plausible. The event must be pharmacologically or phenomenologically definitive, with use of a satisfactory rechallenge procedure if necessary.
- Probably Related – There is evidence to suggest a causal relationship, and the influence of other factors is unlikely. The clinical event, including an abnormal laboratory test result, occurs within a reasonable time after administration of the drug, is unlikely to be attributed to concurrent disease or other drugs or chemicals, and follows a clinically reasonable response on withdrawal (dechallenge). Rechallenge information is not required to fulfill this definition.
- Possibly Related – There is some evidence to suggest a causal relationship (e.g., the event occurred within a reasonable time after administration of the trial medication). However, other factors may have contributed to the event (e.g., the participant’s clinical condition, other concomitant events). Although an AE may rate only as “possibly related” soon after discovery, it can be flagged as requiring more information and later be upgraded to “probably related” or “definitely related,” as appropriate.
- Unlikely to be related – A clinical event, including an abnormal laboratory test result, whose temporal relationship to drug administration makes a causal relationship improbable (e.g., the event did not occur within a reasonable time after administration of the trial medication) and in which other drugs or chemicals or underlying disease provides plausible explanations (e.g., the participant’s clinical condition, other concomitant treatments).
- Not Related – The AE is completely independent of study drug administration, and/or evidence exists that the event is definitely related to another etiology. There must be an alternative, definitive etiology documented by the clinician

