Physical Examination

Blood Pressure

Adverse Event Incidence

Modified Ashworth Scale Score

Population:

Chronic motor-complete paraplegic patients

Phase:

2

Number of Sites

3

enrolling participants:

Description of Study

St. Jude Medical Tripole™ 16 Lead epidural stimulator paddle, extension wire, and Proclaim™ Elite implantable pulse generator

Agent :

[figure not shown]
Study Duration:

5 years

Participant Duration:

15 months

SCHEMATIC OF STUDY DESIGN

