- Epidural hemorrhage, hematoma, spinal cord compression, or paralysis from placement of a lead in the epidural space
- Cerebrospinal fluid (CSF) leakage

- Paralysis, weakness, clumsiness, numbness, or pain below the level of the implant
- Seroma (mass or swelling) at the IPG site
- Allergic or rejection response to implant materials
- Implant migration or skin erosion around the implant

Potential Adverse Effects from Testing

- Skin abrasions
- Muscle damage from transfers
- Injury from Fall
- Hypotension
- Stroke

Participating in this trial is a significant commitment without guarantee of any benefit. Undergoing surgery, rehabilitation, and testing is a significant physical risk. Daily training and monthly appointments garner potential associated economic, social, and psychological risks including required travel for appointments and medical care, dissatisfaction with medical benefit, and prolonged postoperative recovery.

The risks associated with this study are warranted in humans because of the potential direct benefit of the study participants and the spinal cord injury community. There are no known alternative epidural spinal stimulation therapies to offer instead of surgical implantation.

Autonomic Testing

Many SCI subjects will likely sustain skin irritation from the recording electrodes. These conditions are considered to be minimal risks and are reversible.

There is some chance that subjects may sustain lowering or elevation of blood pressure, dizziness or skin abrasion from hand placements of the trainers. If these events occur, the experiment would cease immediately and the principal and co-principal investigators will be alerted if the condition persists. These conditions are considered to be minimal risks and are reversible.

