8 ASSESSMENT OF SAFETY

8.1 SPECIFICATION OF SAFETY PARAMETERS

Safety is not a primary or secondary endpoint of this study but safety is a top concern of the investigators. There is significant experience with epidural spinal cord stimulation amongst the primary and co-investigators for chronic pain and there is significant experience with patients with chronic spinal cord injury. Surgical risk, while low, represents the largest aspect of safety concern for this study. Safety during follow-up testing is also a significant concern as it relates to dysautonomia and falls.

While adverse events will be queried at each appointment and serious adverse events will be monitored and reported, there are specific risk parameters that will be monitored conscientiously during the following time periods:

Perioperative

- Hypotension and hemodynamic instability

- Infection
- Bleeding
- Pain
- Cerebrospinal fluid leak

Follow-up Visits

- Hypotension
- Surgical site infection and seroma

These events will be anticipated and, if found, will be recorded in the adverse event database for review. The Adverse Event Incidence Endpoint will reflect the increased vigilance for these safety outcomes.

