8.5 STUDY HALTING RULES

Use and implantation of the neurostimulator system will be halted when three grade 3 AEs determined to be “probably related or definitely related.” The PI will notify the study sponsor and IRB immediately when the third grade 3 event is reported and enrollment screens will stop accepting new study participants. The study sponsor will inform the FDA of the temporary halt and the disposition of the study.

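### The adverse event causality grades use drug-withdrawal criteria that do not fit implant surgery or study testing, so the 8.5 halting rule may undercount those harms

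*Combined protocol and SAP*

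**What the plan says.** The Protocol Summary describes the study agent as hardware: "16 Lead epidural stimulator paddle, extension wire, and Proclaim" pulse generator. Section 6.1.4 has it placed through a laminectomy. There is no study drug.

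Section 8.2.2 tells the examining clinician to judge "causality based on temporal relationship and his/her clinical judgment", and then to grade certainty on five defined categories. Their vocabulary is that of a drug trial: drug administration, trial medication, other drugs or chemicals, dechallenge, rechallenge.

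- Definitely related: "The response to withdrawal of the drug (dechallenge) should be clinically plausible". It adds: "The event must be pharmacologically or phenomenologically definitive, with use of a satisfactory rechallenge procedure if necessary".
- Probably related: the event has reasonable timing, "is unlikely to be attributed to concurrent disease or other drugs or chemicals, and follows a clinically reasonable response on withdrawal (dechallenge").
- Possibly, unlikely and not related: no withdrawal criterion.

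Section 8.1 ranks the risks: "Surgical risk, while low, represents the largest aspect of safety concern for this study". It also names dysautonomia and falls during follow-up testing. Section 2.3.1 lists testing harms such as "Muscle damage from transfers", skin abrasion and injury from a fall.

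Section 8.5 states: "Use and implantation of the neurostimulator system will be halted when three grade 3 AEs determined to be" probably or definitely related. Section 10.4.4 will describe each adverse event by, among other things, its relationship grade.

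**The concern.** A laminectomy cannot be withdrawn. If a subject has an epidural haematoma or a CSF leak and keeps the device, there is no dechallenge to observe, however plain the surgical cause. The same holds for a fracture or abrasion during assisted standing, because switching the stimulator off does not test what caused it. A clinician who applies the written definitions will find that such an event does not meet probably related and fits definitely related only by a generous reading.

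The scale also rates relation to the study agent only. It never asks whether the operation, the anaesthetic or a study test caused the event.

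At stake are the one numerical halting rule in the protocol and the relationship column in the safety tables. Both take their input from this scale, and both could understate the harms that section 8.1 puts first. Safety oversight rests with the principal investigator alone (8.6), so the protocol provides no independent committee that would routinely catch a grading problem.

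**Working it through.** No power, alpha or sample size figure is involved. The check sets the causality grades beside the halting rule.

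| Grade (8.2.2) | Withdrawal criterion | Counted by 8.5 |
|---|---|---|
| Definitely | Yes (should be plausible) | Yes |
| Probably | Yes (joined by *and*) | Yes |
| Possibly | No | No |
| Unlikely | No | No |
| Not related | No | No |

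1. Two of five grades carry the withdrawal criterion, and exactly those two feed the halting rule.

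2. Take an epidural haematoma needing reoperation, which is the protocol's own example of a serious event (8.1.2), with the device kept in place. Timing fits and other causes are unlikely, but the third element of probably related has nothing to be assessed against. For definitely related, the weaker verb and the option of a phenomenologically definitive event leave room. The event could then satisfy the higher grade while failing the lower one, which is a recipe for disagreement across the three sites.

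3. Illustrative effect on the count. Suppose three subjects have such an event and each is accepted as grade 3.
   - Strict reading, all held at possibly related: 3 × 0 = 0 towards the threshold of three.
   - Judgment-led reading, all graded probably or definitely: 3 × 1 = 3, and the threshold is met.
   - Mixed grading across sites: 1 or 2.

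   The same facts give any value from 0 to 3.

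4. Frequency. Section 2.3.1 places epidural haematoma in the group headed rare (under 1 in 100) or low impact. If it is under 1 in 100, fewer than 56 × 0.01 = 0.56 events would be expected in the planned 56 subjects. The example therefore shows how the rule works and is not a forecast. The count pools all qualifying events, not haematomas alone.

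5. Causal target. Section 8.1.3 asks whether harm may have been caused by the research procedures. Sections 8.2.2 and 8.3 ask about the study agent or product. A transfer injury during a standing test is plainly related under 8.1.3 but has no clear place in 8.2.2. It could even be argued into not related, with the transfer itself documented as the other cause.

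6. Where the criterion does work. Unwanted sensation or movement from stimulation can be tested by switching off, and an event that resolves after explantation has a dechallenge of a kind. The misfit is confined to surgical events with the device retained and to testing events.

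**The case against.** The strongest reply is that 8.2.2 opens with timing and clinical judgment. Withdrawal is one criterion among several, definitely related says only that a plausible response should be present, rechallenge applies only if necessary, and possibly related can be upgraded. An operative-site haematoma with no competing cause also fits possibly related poorly, since that grade supposes other contributing factors. Section 8.5 halts implantation as well as use, which suggests that surgical harm was meant to count. All of this stands, and it makes the defect one of ambiguity and likely under-grading, not a bar. It does not remove the defect: judgment is exercised within the listed definitions, and an upgrade can lead only to the two grades that carry the withdrawal criterion.

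A reader might infer that surgical and testing harms cannot be graded probably or definitely related, or that no study action follows without those grades. The documents do not support either. Serious events go to the IRB and FDA within 24 hours whatever the cause (8.4.2). All adverse events are reported within 30 days (8.4.1). Unanticipated problems need only a possible relation to participation (8.1.3). Recruitment stops after subject 10 until FDA has reviewed safety (5.3). The study may be suspended for unacceptable risk (5.5). Nor does the prompt IRB reporting in 8.4.3 inherit the fault: it rests on the principal investigator's opinion and does not cite the 8.2.2 grades.

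These safeguards make undetected harm unlikely. They do not repair the halting count: reporting is not halting, the FDA pause happens once, and suspension under 5.5 is discretionary.

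On testing events, not related also demands a documented alternative cause, and a fall during stimulated standing is not readily independent of the device. What stands is narrower: the scale never asks about the test procedure.

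**Conclusion.** The point holds in a limited form. Section 8.2.2 is written for a drug, and its withdrawal criterion does not fit surgical events with the device in place or injuries during testing. Such events are likely to be under-graded or graded inconsistently, may be missed by the 8.5 rule, and may be misclassified in the 10.4.4 summary. The affected part is two of five grades and one halting rule; three such events could add 0 to 3 to the count.

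This rests on three assumptions: clinicians apply the definitions broadly as written; the device stays in; and the events reach grade 3. The last cannot be settled from the text, because 8.2.1 gives only mild, moderate and severe and refers to a grading system that the available text does not contain.

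The change should be made. It is not a claim that harm would go unreported.

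**What to change.** Replace the drug terms in 8.2.2 with wording that covers the implant procedure and anaesthesia, the device, stimulation, and study testing or training. Base the grades on timing, mechanism or site, and the absence of a more likely cause. Apply dechallenge only where stimulation can be switched off. Then reconcile 8.2.2 with 8.1, 8.5 and 10.4.4 so that all four use the same causal target, and revise the adverse event form to match.

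Which events should count towards halting is for the sponsor to state when reconciling 8.2.2 with 8.5; this point proposes no change to the threshold. Separate ratings for each source of harm are one way to lay out the form, but are not needed to cure the mismatch.

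The cost is protocol and form wording, a slightly longer form, and probably more events rated related.

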8.2.3 EXPECTEDNESS

The principal and co-principal investigators will be responsible for determining whether an AE is expected or unexpected. An AE will be considered unexpected if the nature, severity, or frequency of the event is not consistent with the risk information previously described for the study agent.

8.3 TIME PERIOD AND FREQUENCY FOR EVENT ASSESSMENT AND FOLLOW-UP

The occurrence of an AE or SAE may come to the attention of study personnel during study visits and interviews of a study participant presenting for medical care, or upon review by a study monitor. All AEs including local and systemic reactions not meeting the criteria for SAEs will be captured on the appropriate CRF. Information to be collected includes event description, time of onset, clinician's assessment of severity, relationship to study product (assessed only by those with the training and authority to make a diagnosis), and time of resolution/stabilization of the event. All AEs occurring while on study must be documented appropriately regardless of relationship. All AEs will be followed to adequate resolution.

Any medical condition that is present at the time that the participant is screened will be considered as baseline and not reported as an AE. However, if the study participant's condition deteriorates at any time during the study, it will be recorded as an AE. UPs will be recorded in the data collection system throughout the study. Changes in the severity of an AE will be documented to allow an assessment of the duration of the event at each level of severity to be performed. AEs characterized as intermittent require documentation of onset and duration of each episode. The PI will record all reportable events with start dates occurring any time after informed consent is obtained until 7 (for non-serious AEs) or 30 days (for SAEs) after the last day of study participation. At each study visit, the investigator will inquire about the occurrence of AE/SAEs since the last visit. Events will be followed for outcome information until resolution or stabilization.

8.4 REPORTING PROCEDURES

8.4.1 ADVERSE EVENT REPORTING

All adverse events will be collected and report to the IRB and sponsor regularly and within 30 days.

8.4.2 SERIOUS ADVERSE EVENT REPORTING

AEs will be followed until resolution even if this extends beyond the study-reporting period. Resolution of an AE is defined as the return to pretreatment status or stabilization of the condition with the expectation that it will remain chronic.

Any AE that meets a protocol-defined serious criterion must be submitted immediately (within 24 hours of site awareness) on an SAE form to the IRB and FDA. The principal investigator will be notified of the SAE by the FDA. The principal investigators monitor will review and assess the SAE for regulatory reporting and potential impact on study subject safety and protocol conduct.

At any time after completion of the study, if the investigator becomes aware of an SAE that is suspected to be related to study product, the investigator will report the event to the IRB and FDA.

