8.2 CLASSIFICATION OF AN ADVERSE EVENT

8.2.1 SEVERITY OF EVENT

For AEs not included in the protocol defined grading system, the following guidelines will be used to describe severity

- Mild – Events require minimal or no treatment and do not interfere with the participant’s daily activities.
- Moderate – Events result in a low level of inconvenience or concern with the therapeutic measures. Moderate events may cause some interference with functioning.
- Severe – Events interrupt a participant’s usual daily activity and may require systemic drug therapy or other treatment. Severe events are usually potentially life-threatening or incapacitating.

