8.6 SAFETY OVERSIGHT

Safety oversight will be the responsibility of the principal investigator.

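### Section 8.4.2 makes the FDA the PI's stated source of SAE notice, with no time limit and no site-to-PI step, although the PI holds safety oversight and must act at once on the halting rule

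*Combined protocol and SAP*

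**What the plan says.** Under 8.4.2, an event that meets a seriousness criterion "must be submitted immediately (within 24 hours of site awareness) on an SAE form to the IRB and FDA". The PI is not named as a recipient. The next sentence supplies the PI's notice: "The principal investigator will be notified of the SAE by the FDA". The sentence after that has the PI's monitor review the SAE for its regulatory and safety implications.

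Section 8.6 reads: "Safety oversight will be the responsibility of the principal investigator". Section 8.5 sets the halting rule: "Use and implantation of the neurostimulator system will be halted when three grade 3 AEs determined to be" probably or definitely related. It continues: "The PI will notify the study sponsor and IRB immediately when the third grade 3 event is reported".

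For AEs in general, 8.4.1 states: "All adverse events will be collected and report to the IRB and sponsor regularly and within 30 days".

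Section 8.2.1 defines Mild, Moderate and Severe without numbers and introduces them as follows: "For AEs not included in the protocol defined grading system, the following guidelines will be used to describe severity". No such grading system appears in the protocol text, and grade 3 is used only in 8.5.

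**The concern.** The person responsible for safety oversight is placed at the end of the SAE chain, behind a regulator whose timing the protocol does not control. The study has three sites. Section 12.1 makes a designated co-investigator at each site the surgeon of record for the implantations there, and 8.2.2 has the examining clinician judge relatedness. A surgical or device complication may therefore be known, and judged related, at one site before the PI hears of it. Section 8.5 sets no per-site count, so someone has to add events across sites.

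At stake is prompt use of the halting rule. It covers stimulation as well as new implants, and 7.1.1 allows implanted subjects up to four hours of stimulation a day at home. Section 5.3 provides an FDA checkpoint after the first 10 subjects, and 5.5 allows suspension for unacceptable risk at any time. After the checkpoint, 8.5 is the only stop based on a count of events in a planned sample of at least 56 (10.5).

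**Working it through.** No formula applies. The check sets out every route by which an event might reach the PI and asks whether it has a time limit that ends with the PI.

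| Route | Who receives it | Time limit |
|---|---|---|
| SAE form, 8.4.2 | IRB and FDA | 24 hours after the site learns of it |
| FDA notice, 8.4.2 | PI | None |
| Monitor's SAE review, 8.4.2; safety review, 10.4.7.1 | Monitor, then the PI for analysis | None |
| Expectedness decision, 8.2.3 | PI and co-PIs | None |
| Recording of events, 8.3 | PI | None; the 7 and 30 days given there define how long after participation events are collected |
| General AE reporting, 8.4.1 | IRB and sponsor | 30 days |
| Unanticipated problems, 8.4.3 | IRB | 5 days or 10 business days |
| Events during autonomic or standing tests, 2.3.1 | PI and co-PI | None; limited to testing events |

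**SAEs.** The only limit specific to SAEs is 24 hours, and it ends at the IRB and FDA. Every route that ends with the PI lacks a limit for telling the PI.

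**Severe, related, non-serious AEs.** The 8.5 trigger is a severity grade, whereas the 24-hour rule depends on seriousness. The two sets overlap but differ. Section 8.2.1 describes a Severe event as one that interrupts the participant's "usual daily activity and may require systemic drug therapy or other treatment". An event can fit that description without meeting any criterion in 8.1.2. It then has only the 30-day limit of 8.4.1, to the IRB and sponsor. The same definition adds that Severe events usually threaten life or incapacitate, and such events would mostly be serious too. This second gap is therefore the exception.

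**Whether 8.4.3 closes either gap.** Its limits run to the IRB. Its AE item covers events that the PI considers both unexpected and related. Complications listed in 2.3.1, such as infection or CSF leak, would usually count as expected under 8.2.3.

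**The trigger.** Section 8.5 counts grade 3 events, and 8.2.1 has three unnumbered levels. Severe is the natural equivalent, as the third and highest level, but the protocol does not say so.

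**The case against.** The strongest reply is that the FDA is not the PI's only channel. The monitor is chosen by the PI (13.5) and reviews each SAE. The PI and co-PIs must see an AE before they can class it as expected, so meeting the 8.4.3 limits presupposes some earlier review, including of events later set aside as expected. The surgeon of record is a co-investigator. SAEs still reach the IRB and FDA within 24 hours. All of this stands and makes the gap smaller. None of it sets a time by which the PI must know.

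The PI may also be the sponsor, since section 11 and others speak of an investigator-sponsor. If so, 8.4.1 reports reach the PI directly, but still with a 30-day limit, and 8.4.2 does not send the SAE form to the sponsor. Section 8.5 has the PI notify the sponsor, as if they were separate.

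A reader might infer three stronger claims that the documents do not support:

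- *That 8.4.2 and 8.5 contradict each other because the PI alone starts the halt.* The first sentence of 8.5 imposes the halt without naming who acts. The PI's stated duty is to notify, and it runs from the report of the third event. What is missing is an earlier step.
- *That the PI will learn of halting events up to 30 days late.* The 30 days are an outer limit to the IRB and sponsor. They do not measure delay to the PI.
- *That the harm can be expressed as implants performed during a delay.* That would need the delay to the PI and the rate of qualifying events. The documents give neither.

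**Conclusion.** The concern holds in a limited form. Followed as written, 8.4.2 leaves the PI's SAE notice to the FDA without a time limit, and no other section sets a time for a site to tell the PI. That fits poorly with sole safety oversight in 8.6 and an immediate duty in 8.5. The smaller gap for Severe, related, non-serious AEs also holds, as an exception. The undefined grade 3 is a minor wording point.

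The size of the effect cannot be estimated. The conclusion assumes that the halting count is study-wide and that no separate procedure sets a site-to-PI limit. A manual of procedures exists but was not among the documents. The FDA sentence may be a drafting slip. It should be corrected either way, because sites would follow the text as it stands. The threshold of three is not in question.

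**What to change.** - **8.4.2:** replace the sentence in which the FDA notifies the PI with: *The site will notify the PI within 24 hours of awareness of every SAE and of every Severe AE judged probably or definitely related.* Keep the report to the IRB and FDA as it is.
- **8.4.1:** add the matching exception to the 30-day limit for Severe AEs judged probably or definitely related.
- **8.5:** replace grade 3 with *Severe (8.2.1)* in both places.
- **8.2.1:** as a tidy-up, supply the grading system it refers to or remove the reference.

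The cost is these wording changes and one extra notice from site to PI per qualifying event. Visits, sample size, analysis and the halting threshold do not change.
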